7.2 Unscheduled or Early Termination Visits

For an unscheduled visit occurring after the first dose date of IP, the unscheduled visit will be mapped into the closest post-baseline study scheduled visit for the assessment based on the study day of the unscheduled visit, and the target study day of the scheduled visit of the assessment in the protocol. If the unscheduled visit has the equal distance to the 2 study scheduled visits, it will be mapped to the later one.

The unscheduled visit will be only mapped to the study visit within each study period during which it occurs. If an unscheduled visit occurs during the Open-Label Treatment Period (from the first dose date to the dose date at week 48), it should be mapped to the study visit in the Open-Label Treatment Period. If an unscheduled visit occurs after the dose date at week 48 and in the Treatment Extension Period, it should be mapped to the study visit in the Treatment Extension Period.

When there is more than one measurement mapped to the same scheduled visit (including the original measurement taken from the scheduled visit), the measurement taken on the scheduled visit will be used if it is not missing, otherwise the one closest to the target day will be used. If more than one visit has the equal distance to the target day then the later one will be used. If more than one measurement is collected on the same day, use the time or the sequence number to select the latest record. For listings and shift tables, all data points will be included.

Early termination visit will follow the same rule for unscheduled visit as described above.

The bone biopsy taken in the early termination visit will not be mapped to the study scheduled visit as the bone biopsy will be only taken either on week 48 or at the early termination visit post-baseline used in the analysis.

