### **7.3.3 Removal of Subjects from Therapy or Assessment**

In accordance with the Declaration of Helsinki, subjects have the right to withdraw from the study at any time for any reason. The investigator and Ultragenyx also have the right to remove subjects from the study. Ultragenyx must be notified of all subject withdrawals as soon as possible. Ultragenyx also reserves the right to discontinue the study at any time for either clinical or administrative reasons and to discontinue participation of an individual subject or investigator due to poor enrollment or noncompliance, as applicable.

Subjects may be removed from the study for the following reasons:

- Occurrence of an unacceptable AE
- An illness that, in the judgment of the investigator or Ultragenyx, might place the subject at risk or invalidate the study
- Pregnancy in subject
- At the request of the subject, investigator, or Ultragenyx, for administrative or other reasons
- Protocol deviation or noncompliance

If the reason for removal of a subject from the study is an AE, the AE and any related test or procedure results will be recorded in the source documents and transcribed onto the Case Report Form (CRF). Each clinically significant abnormal laboratory value or other clinically meaningful abnormality should be followed until the abnormality resolves or until a decision is made that it is not likely to resolve. If such abnormalities do not return to normal within 30 days after the last dose given, their etiology should be identified and Ultragenyx should be notified. All unscheduled tests must be reported to Ultragenyx immediately.

If a subject discontinues from the study prematurely, every reasonable effort should be made to perform the Early Termination Visit procedures within four weeks of discontinuation. Subjects who discontinue due to SAE will be monitored for safety through the final Safety Follow-up TC (as defined in Section 7.4.3.1).

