4.2 Key Secondary Efficacy Endpoint

The key secondary efficacy endpoint is the proportion of subjects achieving mean serum phosphorus levels above the lower limit of normal (LLN; 2.5 mg/dL [0.81 mmol/L]) at the mid-point of the dose interval (i.e., Weeks 2, 6, 14, and 22), as averaged across dose cycles between baseline and Week 24.

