8.6.2 Key Secondary Efficacy Endpoint

The key secondary efficacy endpoint is the proportion of subjects achieving mean serum phosphorus levels above the LLN (2.5 mg/dL [0.81 mmol/L]) at the mid-point of the dose interval (i.e., Weeks 2, 6, 14, and 22), as averaged across dose cycles between baseline and Week 24.

The number and proportion of subjects achieving mean serum phosphorus levels above the LLN (2.5 mg/dL [0.81 mmol/L]) will be summarized and the two-sided 95% confidence interval will be provided for the proportion. The Wilson score method ([Wilson 1927](#)) will be

applied to estimate the confidence interval. The p-value for testing the proportion of subjects achieving the mean serum phosphorus levels above the LLN (2.5 mg/dL [0.81 mmol/L]) against 0% from the binomial test will also be provided.

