8.6.3.2 Key PD

Descriptive summaries of the following secondary PD endpoints will be provided.

- Proportion of subjects achieving mean serum phosphorus levels above the LLN (2.5 mg/dL [0.81 mmol/L]) at the end of the dosing cycle (4 weeks after dosing), as averaged across dose cycles between baseline and week 24.
- Mean change from baseline and percent change from baseline in serum phosphorus at each mid-point of dosing cycle, as averaged across dose cycles between baseline and week 24.
- Mean change from baseline and percent change from baseline in serum phosphorus at each end of dosing cycle, as averaged across dose cycles between baseline and week 24.
- Time-adjusted area under the curve (AUC) of serum phosphorus between baseline and week 24.

Observed values and change from baseline, serum intact FGF23, percent change from baseline over time in serum phosphorus, 1,25(OH)₂D, and urinary phosphorus, TRP, TmP/GFR, and FEP will be summarized at each milestone analysis.

The change from baseline over time for key PD will be analyzed using the GEE model as described in Section 8.1, if the model converges.

A listing for the PD parameters will be provided.

Mean (\pm SE) PD-time plots may be presented for the PD parameters.

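### SAP 7.2 can fill a missing mid-point or end-of-cycle phosphorus value with an unscheduled or early-termination draw chosen by study day alone, whatever the time since dose (minor)

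*SAP*

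**What the plan says.** SAP 7.2 assigns post-dose unscheduled values by study day: "the unscheduled visit will be mapped into the closest post-baseline study scheduled visit for the assessment". Ties go to the later visit. A scheduled result has priority: "the measurement taken on the scheduled visit will be used if it is not missing". Otherwise the mapped value nearest the target day is taken. ET visits are treated alike: "Early termination visit will follow the same rule for unscheduled visit as described above". Two limits are stated. A value stays within its own study period, and one assessment is exempt: "The bone biopsy taken in the early termination visit will not be mapped to the study scheduled visit".

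The phosphorus endpoints depend on cycle phase. SAP 4.2 defines the key secondary endpoint by the subject's mean level "at the mid-point of the dose interval (i.e., Weeks 2, 6, 14, and 22), as averaged across dose cycles between baseline and Week 24". SAP 8.6.3.2 defines its counterpart "at the end of the dosing cycle (4 weeks after dosing), as averaged across dose cycles between baseline and week 24". SAP 7.1.1 counts a subject as not achieving the lower limit of normal (LLN) only when there are no serum data for the key secondary endpoint.

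On ET timing, Protocol 7.3.3 says "every reasonable effort should be made to perform the Early Termination Visit procedures within four weeks of discontinuation". SAP Appendix 1 includes ET among the phosphorus sampling times.

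**The concern.** The mid-point and end-of-cycle endpoints differ only in when, within the 28-day cycle, phosphorus is measured. Protocol 7.4.3 reports that phosphorus fell late in the interval as drug levels declined. A substitution rule that looks only at study day can therefore enter a late-cycle or off-drug value as a mid-point, or a mid-cycle value as an end-of-cycle result. SAP 7.1.1 does not prevent this, because once a value has been mapped the subject has data.

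The affected subjects are those with missed samples or early withdrawal. What is at stake is the reported proportion and its interval in a study of 14.

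**Working it through.** **Inputs.** Study Day 1 is the first dose (SAP 5.3), so the target day for Week k is 7k + 1. Phosphorus visits through Week 28 are Weeks 1, 2, 4, 6, 12, 14, 20, 21, 22, 24 and 28 (SAP Appendix 1 and Appendix 5). Dosing is every 28 days, so on-schedule doses fall on Days 1, 29, 57, 85, 113, 141 and 169. A draw on a dosing day is taken as pre-dose. The SAP does not list the end-of-cycle weeks; from the schedule I take Weeks 4, 12, 20 and 24. The plan states no figure to reproduce here.

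**Step 1: days captured by each visit under the literal rule.** Each day goes to the nearest phosphorus visit, ties to the later one.

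| Visit | Target day | Days captured | Largest distance | Days after a dose |
|---|---|---|---|---|
| Week 2 | 15 | 12-21 | 6 | 11-20 |
| Week 6 | 43 | 36-63 | 20 | 7-28, then 1-6 |
| Week 14 | 99 | 92-119 | 20 | 7-28, then 1-6 |
| Week 22 | 155 | 152-161 | 6 | 11-20 |
| Week 12 | 85 | 64-91 | 21 | 7-28, then 1-6 |
| Week 20 | 141 | 120-144 | 21 | 7-28, then 1-3 |

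The wide windows arise because no phosphorus is scheduled at Weeks 8, 10, 16 or 18.

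**Step 2: how much of the Week 6 and Week 14 windows is out of phase.** This depends on the tolerance, which is an assumption.
- Accept 4-24 days after a dose (14 days, with ±5 on the dose visit and ±5 on the draw). For Week 6, Days 36-53 and 61-63 qualify: 18 + 3 = 21 of 28, leaving 7 of 28 (25%) out of phase.
- Require 9-19 days (14 ± 5). Days 38-48 qualify: 11 of 28, leaving 17 of 28 (61%) out of phase.

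Week 14 gives the same counts. Weeks 2 and 22 are essentially protected: 10 of 10 days qualify on the wider band and 9 of 10 on the narrower. At Weeks 12 and 20, 11 captured days in each window are mid-cycle, 9-19 days after a dose (Days 66-76 and 122-132).

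**Step 3: the ET route.** Assume the subject discontinues before the next dose is due and the ET visit follows within 28 days, so the draw is at most 28 + 28 = 56 days after the last dose.
- Last dose Week 0 (Day 1): draws on Days 36-57 become Week 6, at 35-56 days after the dose.
- Last dose Week 8 (Day 57): draws on Days 92-113 become Week 14, at 35-56 days.
- Last dose Week 16 (Day 113): draws on Days 152-161 become Week 22, at 39-48 days.
- Last dose Week 4 (Day 29) or Week 12 (Day 85): draws on Days 36-63 or 92-119 become Week 6 or 14, at 7-34 days, some in phase and some not. Later draws, at 35-56 days, become end-of-cycle Week 12 or 20.

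**Step 4: effect on one subject's mean.** Assume a simple mean of the available mid-point values. A substitute lower than the others by a gap g lowers an n-value mean by g/n. The documents give no trough or off-drug figure, so g is assumed. Protocol 7.4.3's maximum rise of about 1 mg/dL is used as the off-drug upper end.
- Off-drug ET value, g = 0.25-1.0 mg/dL: 0.13-0.50 at Week 6 (n = 2), 0.08-0.33 at Week 14 (n = 3), 0.06-0.25 at Week 22 (n = 4).
- On-drug late-cycle value, g = 0.1-0.5 mg/dL, n = 4: 0.03-0.13.

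Status changes only if the mean without the substitute lies above 2.5 mg/dL by no more than that amount. For example, three values of 2.6 and a substitute of 2.1 give (3 × 2.6 + 2.1)/4 = 2.475, against 2.6 if the visit is left missing.

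**Step 5: effect on the proportion.** One subject is 1/14 = 7.1 points. Wilson limits are [p + z²/2n ± z√(p(1−p)/n + z²/4n²)]/(1 + z²/n), with z = 1.96 and n = 14. For 14/14 this gives 78.5-100%. For 13/14 the centre is 0.836 and the half-width 0.151, giving 68.5-98.7%.

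**The case against.** **The endpoint wording already fixes the phase, so a programmer could read it as limiting SAP 7.2.** This does not stand. Nothing in SAP 7.1.1, 7.2 or the endpoint sections restricts the mapping, and the endpoint names weeks, to which SAP 7.2 assigns values.

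**The ±5-day tolerance is not a protocol definition of phase.** This stands. The visit window applies to dosing visits as well as draws, so a compliant scheduled mid-point sample may itself be 4-24 days after a dose. A reader might infer that 61% of possible Week 6 and Week 14 substitutes are wrong by the protocol's own standard; on the wider band it is 25%. Both figures count days in a window and are not probabilities of an error.

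**The on-drug route is improbable.** This stands. It needs a missed sample and an extra draw at the wrong point of the same window. Protocol 7.4.1 mentions unscheduled phosphorus alongside dose adjustment, which it considers unlikely. Protocol 7.5.3.8 also allows extra safety samples after certain adverse events, but the scheduled value must still be missing.

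**For the key secondary endpoint, the errors of known direction are conservative.** This stands. A reader might infer that the rule flatters the drug on that endpoint. The documents do not support that: late-cycle and off-drug values lower the mid-point proportion, and no direction can be given for early-cycle values. Mid-cycle values would raise the end-of-cycle result, and off-drug ET values would lower it.

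**Little depends on it.** This stands. The primary endpoint is histomorphometric and the ET biopsy is exempt, p-values are nominal, and SAP 3.4 places the powered phosphorus evidence in UX023-CL303. SAP 7.2 keeps all data points in listings, though no section asks for days since dose.

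**Conclusion.** The gap is real and minor. As written, SAP 7.2 can place a phosphorus value from the wrong part of the cycle, or from after treatment has lapsed, into endpoints defined by cycle phase. The exposed mid-points are Weeks 6 and 14, plus Week 22 for a subject whose last dose was at Week 16. Early termination is the more plausible route.

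The effect is zero if scheduled values are present, since those are never overwritten, and its frequency cannot be derived from the documents. It also requires a subject close above 2.5 mg/dL. If one such subject changes status, the proportion moves 7.1 points and the lower Wilson limit falls from 78.5% to 68.5%. The p-value "against 0% from the binomial test will also be provided" does not depend on this: a single success is impossible under a true proportion of zero, so 14/14 and 13/14 are alike for it.

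The conclusion rests on on-schedule dosing, ET within four weeks of discontinuation, a simple mean of available values and the assumed gaps in mg/dL. A reader might also take the missing distance limit to mean that any distance is possible. The nearest-visit rule itself caps it at 20-21 days for Weeks 6, 12, 14 and 20, which is still most of a 28-day cycle.

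**What to change.** In SAP 7.2, beside the ET biopsy exception, add: for the mid-point and end-of-cycle phosphorus endpoints, an unscheduled or ET value may replace a missing scheduled value only if its days since the last dose fall within a pre-specified band for that visit's phase; otherwise the visit stays missing. An example is 14 ± 5 days for mid-point, and 28 ± 5 days and before the next dose for end of cycle. The band is an analysis choice, not a protocol rule, and should be described as such.

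List days since the last dose for every value used, including scheduled ones, because Protocol 7.4.6 allows late and skipped doses and a scheduled sample can also be out of phase.

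Add one sensitivity analysis of the key secondary proportion that counts subjects who leave before Week 22 as not achieving the LLN. SAP 7.1.1 continues to cover a subject with no mid-point value.

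The cost is one sentence, one variable derived from dates already recorded, and one table row. The downside is that early leavers contribute fewer values and a conservative element leaves the main analysis; the sensitivity row shows how much that matters.

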7.3 Software

SAS[®] software version 9.4 or higher will be used to perform most or all statistical analyses.

8 STATISTICAL METHODS OF ANALYSIS

8.1 General Principles

The statistical analyses will be reported using summary tables, figures, and data listings. Statistical tests will be 2-sided at the $\alpha=0.05$ significance level and 2-sided 95% confidence interval will be used. All p-values will be presented as nominal p-values. No adjustment on multiplicity will be made. Continuous variables will be summarized by number of subjects, mean, standard deviation (SD), standard error (SE), median, Q1, Q3, minimum, and maximum. Categorical variables will be summarized by number and percentages of subjects. No imputation on missing data will be made, unless stated otherwise.

When the sample size and number of observations allow, the change from baseline over time will be analyzed using a generalized estimation equation (GEE) model that includes time as the categorical variable and adjusted for baseline measurement. The covariance structure that will be used for the GEE model is compound symmetry which specifies constant variance for the assessments and constant covariance between the assessments over time. If the number of observations are insufficient for analyses using a GEE model, a t-test will be performed for continuous variables and a 95% confidence interval (CI) of the proportion will be provided for binary variables.

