8.6.3.3 Bone turnover markers

Observed values, change and percent change from baseline over time in serum ALP and biochemical markers of bone turnover, including BALP, CTx, and P1NP, will be summarized at each milestone analysis. A listing will be provided for the biochemical markers of bone turnover.

The change from baseline over time for biomarkers will also be analyzed using the GEE model as described in Section 8.1, if the model converges.

Correlations may be used to assess the relationship between bone turnover markers and selected histomorphometric indices.

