8.6.4 Exploratory Efficacy Endpoints

The number of active (non-healed) pseudofractures and/or fractures as defined by skeletal survey at baseline and the number and percentage of the baseline active pseudofractures/fractures which healed, partially healed, were unchanged or worsened at post-baseline visits will be summarized. New active pseudofractures and/or fractures identified at post-baseline visits will also be summarized.

The number of the subjects with baseline active pseudofractures and/or fractures and the number of those subjects who have changes from baseline to healed, partially healed, unchanged and worsened at post-baseline visits will be summarized. The number of subjects with new active pseudofractures and/or fractures at post-baseline visits will also be summarized.

For BPI (worst pain, pain severity and pain interference), BFI (worst fatigue, and global fatigue score), the observed values, change from baseline over time will be summarized. The change from baseline over time will also be analyzed using the GEE model as described in Section 8.1, if the model converges. Listings for the patient-reported outcomes will be provided.

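### The planned GEE on 14 subjects names no contrast, standard error, small-sample correction or reference distribution, and every uncorrected z-based version of it is anti-conservative

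*SAP*

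**What the plan says.** SAP 8.1 sets two-sided tests at 0.05 with 95% confidence intervals. When the sample size and number of observations permit, change from baseline over time is analysed with a "generalized estimation equation (GEE) model that includes time as the categorical variable and adjusted for baseline measurement". On the covariance it says: "The covariance structure that will be used for the GEE model is compound symmetry which specifies constant variance for the assessments". The fallback reads: "If the number of observations are insufficient for analyses using a GEE model, a t-test will be performed for continuous variables". No number of subjects or observations is given at which the switch happens. The same section states "All p-values will be presented as nominal p-values", without multiplicity adjustment, and plans n, mean, SD and SE for every continuous variable.

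Three later sections call on this model. Key PD in 8.6.3.2 "will be analyzed using the GEE model as described in Section 8.1, if the model converges". In 8.6.3.3 the change "for biomarkers will also be analyzed using the GEE model as described in Section 8.1". For BPI and BFI, 8.6.4 says "The change from baseline over time will also be analyzed using the GEE model as described in Section 8.1". All three add the convergence condition. Appendix 1 lists a descriptive summary and GEE, without a t-test, for PD, bone markers and BPI. Section 7.3 names SAS but no procedure or option.

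Neither the primary endpoint (8.6.1: t-test or sign test) nor the key secondary endpoint (8.6.2: Wilson interval and binomial test) uses GEE.

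**The concern.** There are at most 14 clusters. At that size the choice of SE and reference distribution decides whether a 95% interval covers close to 95%, and the SAP leaves both open.

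Two separate things can go wrong:

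1. **Small sample.** An uncorrected SE with a z reference is too optimistic with 14 subjects, whatever the estimand. The effect is larger for the sandwich SE.
2. **Estimand.** If the visit mean is evaluated at the sample-mean baseline and that mean is treated as fixed, the SE omits its sampling error. This matters if the target is the population mean change. It does not arise if the estimand is conditional on the observed baselines.

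At stake is the apparent precision of the secondary PD and bone-marker results and the exploratory patient-reported outcomes. With complete data the GEE visit mean at the mean baseline equals the raw mean change, so the tables could show one estimate with two different SEs.

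**Working it through.** The documents state no error rate for the GEE, so there is no figure of theirs to reproduce.

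**Inputs from the documents.** n = 14 in one arm (SAP 3.1); two-sided 0.05, categorical time, baseline covariate and compound symmetry (SAP 8.1). Post-baseline visits to Week 48 come from the schedule of events: K = 3 (bone markers), 4 (BPI/BFI), 6 (2-hour urine) and 8 (1,25(OH)2D).

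**Assumptions.** Normal data, complete visits, no true change. Correlation ρ = 0.3, 0.5, 0.8 and post/baseline SD ratio k = 1, 1.5, 2. That gives 4 × 3 × 3 = 36 settings, with 40,000 trials each (Monte Carlo SE 0.1-0.2 points). The test is of zero mean change at the last visit.

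**Step 1: small-sample part, analytic.** Without a correction, the sandwich variance is roughly df/14 of the unbiased one, so the size is about P(|t_df| > 1.96·√(df/14)).
- df = 13: cut-off 1.889, size 8.1%.
- df = 12: cut-off 1.815, size 9.5%.

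**Step 2: estimand part, analytic.** Take baseline SD = 1. The raw change has variance 1 + k² − 2kρ. After regression on baseline the residual variance is k²(1 − ρ²). The large-sample ratio of adjusted SE to true SE is therefore k·√[(1 − ρ²)/(1 + k² − 2kρ)]. For k = 1 this is √[(1 + ρ)/2], and it equals 1 only when kρ = 1.

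| k | ρ = 0.3 | ρ = 0.5 | ρ = 0.8 |
|---|---|---|---|
| 1 | 0.81 | 0.87 | 0.95 |
| 1.5 | 0.93 | 0.98 | 0.98 |
| 2 | 0.98 | 1.00 | 0.89 |

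This part does not shrink as n grows. For k = 1 the limiting size is 11.4%, 9.0% and 6.3% at ρ = 0.3, 0.5 and 0.8.

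**Step 3: simulated size at n = 14, nominal 5%.**

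| Method | Conditional on observed baselines | Population mean change |
|---|---|---|
| Model-based SE, z | 5.6-6.3% | 5.7-12.6% |
| Sandwich SE, z | 8.5-9.0% | 8.5-16.1% |
| Kauermann-Carroll SE, t(12), covariate kept | 4.7-5.1% | 4.8-10.5% |
| Paired t | not the matching test | 4.8-5.3% |

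For sandwich with z and the population target, equal SDs give 15.6-16.1%, 13.2-13.5% and 10.2-10.4% at ρ = 0.3, 0.5 and 0.8; k = 1.5 gives 9.1-10.7% and k = 2 gives 8.5-12.3%. At ρ = 0.1 with equal SDs it is about 19%, so the upper end depends on the assumed range.

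**Step 4: the correction without the covariate.** With visit means only and complete data, each subject's leverage is 1/14. Kauermann-Carroll then multiplies the sandwich variance by 14/13, from Σr²/14² to Σr²/(14·13), which is the paired-t variance. With 13 df the two tests coincide.

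**Step 5: does convergence protect?** A standard GEE routine was run for 2,000 trials in each of 12 settings, with 0% and 10% missing visits. All 24,000 fits converged. Sandwich with z still rejected in 8.2-17.2% (complete) and 10.0-16.1% (10% missing); Monte Carlo SE was 0.4-0.9 points.

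**Step 6: interval width.** Mean paired-t SE over mean sandwich SE was 1.06-1.31, so the sandwich SE is about 6-24% smaller (1 − 1/1.06; 1 − 1/1.31). With t(13) = 2.160, the width ratio is roughly 1.06 × 2.160/1.960 = 1.17 to 1.31 × 2.160/1.960 = 1.44. The simulated widths were 16-45% greater.

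**The case against.** The strongest reply is that the SAP never chooses the sandwich SE. Specifying compound symmetry with constant variance is just as compatible with model-based SEs, and with an estimand conditional on the observed baselines the size is then only about 5.5-6.5%. This stands. A reader might infer that the planned GEE tests have a true error of up to 16%. The documents do not support that: it needs a sandwich SE, a z reference, the population target, equal SDs and a low correlation, none of which is stated. Nor can a larger k be read from the entry criteria, which apply at Screening while PD and the full BPI are measured again on Day -2.

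The second reply is that 8.1 already limits GEE by sample size and provides a t-test, and that the later sections inherit this limit. They do, and the convergence clause adds to the limit without replacing it. But no threshold is given, so the choice is left to the time of analysis.

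The third is that little depends on these results. The p-values are nominal, Protocol 7.6.4.3 asks mainly for summaries, and a reader can rebuild the paired-t interval from the planned n, mean and SE. That limits the harm. But nominal refers to multiplicity; it does not excuse a 95% interval that covers less often.

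The runs also do not span every planned use: serum phosphorus (13 visits to Week 48), iFGF23 (2 visits) and the Week 96 analysis were outside the 36 settings.

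**Conclusion.** The point holds as incomplete specification with a predictable direction of error. Every uncorrected z-based version of the GEE rejects too often at n = 14. The size is about 5.5-6.5% (model-based) or 8.5-9% (sandwich) conditional on baselines, and about 6-13% or 8.5-16% for the population mean change. The population ranges rest on assumed ρ of 0.3-0.8 and k of 1-2, normal data and compound symmetry. Anything above about 9% comes from the estimand and not from the small sample, so a small-sample correction alone does not remove it.

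The SAP should be changed, but the consequence is modest: only nominal secondary and exploratory p-values and intervals are involved. It should not be read as undermining the OV/BV result or the serum phosphorus responder proportion, nor as showing that the GEE must be dropped.

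**What to change.** In SAP 8.1:
- State the contrast (for example, mean change at each visit against zero) and the estimand.
- For any GEE test or interval, require a bias-corrected sandwich SE such as Kauermann-Carroll with a t reference. Use n − 2 df with the baseline covariate if the estimand is conditional on the observed baselines, or n − 1 df without the covariate if the target is the population mean change.
- Report the per-visit paired t-test and its 95% interval, already the SAP's fallback, alongside the GEE as the reference for mean change.

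Align 8.6.3.2, 8.6.3.3, 8.6.4 and the Appendix 1 rows with this rule, so that convergence is no longer the only condition they state. Replacing the GEE outright is optional.

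The cost is SAP wording, minor programming and wider intervals: paired t about 16-45% wider than uncorrected sandwich with z in the assumed settings. The paired t also uses only subjects seen at each visit. With 10% of visits missing completely at random that is 0.9 × 14 = 12.6 on average, and its interval was 0.3-1.4% narrower than an unadjusted Mancl-DeRouen GEE interval. That comparator was conservative with complete data (3.6-4.6%), and Kauermann-Carroll was not run with missing visits, so the precision comparison is only indicative.
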